3.13 End-of-Study Definition

The end of study is defined as the point of final data capture (e.g., the point at which all required data has been collected to answer the research questions in the protocol) or date the study is closed by the Sponsor, whichever occurs first.

After the end-of-study, subjects who are still in survival follow-up part of the study should receive standard of care treatment as determined by their health care provider after completion of the study.

4. STUDY POPULATION

Patients may be considered for enrollment in the study if they meet all the eligibility criteria stated in Sections 4.1 and 4.2. Prospective approval of protocol deviations to recruitment and enrollment criteria, also known as protocol waivers or exemptions, is not permitted.

4.1 Inclusion Criteria

Subjects must meet all the following criteria:

1. Subject has voluntarily agreed to participate by giving written informed consent in accordance with ICH/GCP guidelines and applicable local regulations.
2. Age \geq 18 years.
3. **[PLD Cohort]** Subject has a histologically confirmed diagnosis of high grade EOC (including primary peritoneal cancer or fallopian tube cancer).
NOTE: Non-epithelial tumors and ovarian tumors with low malignant potential are excluded.
4. **[PLD Cohort]** Subject must have platinum-resistant disease, defined as disease progression within 180 days (6 months) following the last administered dose of platinum therapy.
NOTE: Progression should be calculated from the date of the last administered dose of platinum therapy to the date of the radiographic imaging showing progression.
NOTE: Subjects who are primary platinum refractory, defined by progressing during or within 1 month of upfront platinum therapy, are excluded.

5. **[PLD Cohort]** Subjects may have received any number of prior lines of therapy for EOC; however, they may not have received more than 1 prior line of systemic anticancer therapy for platinum-resistant disease.

Lines of therapy are defined in this study as:

- Adjuvant \pm neoadjuvant is considered 1 line of therapy.
- Maintenance therapy (e.g., bevacizumab, PARP inhibitors) will be considered part of the preceding line of therapy (i.e., not counted independently).
- Therapy changed due to toxicity in the absence of progression will be considered part of the same line (i.e., not counted independently).
- Hormonal therapy will be counted as a separate line of therapy unless it was given as maintenance.

6. **[MIRV Cohort]** Subject has a histologically confirmed diagnosis of high grade serous EOC (including primary peritoneal cancer or fallopian tube cancer).

NOTE: non-epithelial tumors and ovarian tumors with low malignant potential are excluded.

7. **[MIRV Cohort]** Subject must have platinum-resistant disease as defined by:

- Subjects who have only had 1 line of platinum-based therapy must have received at least 4 cycles of platinum, must have had a response (complete response/remission [CR] or partial response/remission [PR]) and then progressed between > 3 months and \leq 6 months after the date of the last dose of platinum.
- Subjects who have received 2 or 3 lines of platinum therapy must have progressed on or within 6 months after the date of the last dose of platinum.

NOTE: Progression should be calculated from the date of the last administered dose of platinum therapy to the date of the radiographic imaging showing progression.

NOTE: Subjects who are platinum refractory during front-line treatment are excluded [primary platinum-refractory disease, defined as disease that did not respond to (CR or PR) or has progressed within \leq 3 months of the last dose of first-line platinum-containing chemotherapy].

8. **[MIRV Cohort]** Subjects must have received at least 1 but no more than 3 prior systemic lines of anticancer therapy.

Lines of therapy are defined in this study as:

- Adjuvant \pm neoadjuvant is considered 1 line of therapy.
- Maintenance therapy (e.g., bevacizumab, PARP inhibitors) will be considered part of the preceding line of therapy (i.e., not counted independently).
- Therapy changed due to toxicity in the absence of progression will be considered part of the same line (i.e., not counted independently).
- Hormonal therapy will be counted as a separate line of therapy unless it was given as maintenance.

9. **[MIRV Cohort]** Willing to provide an archival tumor tissue block or slides or undergo new biopsy using a low-risk, medically routine procedure for IHC confirmation of FR α positivity.

10. **[MIRV Cohort]** Subject's tumor must be positive for FR α expression defined as PS2+ \geq 25% by the Ventana FOLR1 Assay.

11. Eastern Cooperative Oncology Group Performance Status (ECOG PS) of 0 or 1.

12. Measurable disease by RECIST v1.1 using radiologic assessment.

13. Laboratory values must meet the following criteria.

Laboratory parameter	Threshold value
Absolute neutrophil count (ANC)	$\geq 1.5 \times 10^9/L$ without GCSF in prior 10 days or long-acting WBC growth factors in prior 20 days
Platelet count	$\geq 100 \times 10^9/L$ without platelet transfusion in prior 10 days
Hemoglobin (Hgb)	$> 9.0 \text{ g/dL}$ without packed RBC transfusion in the prior 7 days
Creatinine clearance (CrCl)	$\geq 30 \text{ mL/min}$ (using modified Cockcroft-Gault formula; Appendix Section 16.3)
ALT/AST	$\leq 3 \times \text{ULN}$
Total bilirubin	$\leq 1.5 \times \text{ULN}$; subjects with isolated indirect hyperbilirubinemia are permitted if direct bilirubin ratio is $< 35\%$ and total bilirubin is $\leq 3.0 \times \text{ULN}$
Serum albumin [MIRV cohort only]	$\geq 2 \text{ g/dL}$
Left ventricular ejection fraction (LVEF) [PLD Cohort only]	$> 50\%$ by ECHO/MUGA

14. Females of childbearing potential (FCBP) must have a negative serum or urine pregnancy test within 4 days of the first dose of study treatment. FCBP must use 2 highly effective methods of contraception starting at least 14 days prior to the first dose of study treatment, throughout the study, and for at least 6 months (or for the duration required by local regulatory guidance) after the last dose of PLD or at least 3 months after the last dose of SL-172154 or MIRV, whichever is longer. See Appendix Section 16.2 for further details regarding effective methods of contraception.
15. Subjects must have stabilized or recovered (Grade 1 or baseline) from all prior anti-cancer therapy-related toxicities. NOTE: Grade 2 alopecia is acceptable for either cohort; Grade 2 sensory neuropathy [PLD Cohort only] or Grade 1 sensory neuropathy [MIRV Cohort only] is acceptable.
16. [MIRV Cohort only, Dose Expansion only] Willing to consent to 1 mandatory pretreatment and 1 on-treatment tumor biopsy, unless there is excessive risk from the procedure as determined by the investigator.

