- i. **Pregnancy Test:** A serum pregnancy test (beta-human chorionic gonadotropin [β -hCG]) or urine pregnancy test must be performed at screening for all FCBP within 4 days of the first dose of PLD on Cycle 1 Day 1. Repeat this test every 8 weeks during study treatment (i.e., C3D1, C5D1, C7D1, etc.) and at PTV. Contraception should be continued for at least 6 months (or for the duration required by local regulatory guidance) after the last dose of PLD or 3 months after the last dose of SL-172154, whichever is longer.
- j. **Hematology/ Clinical Chemistry/ Coagulation/ TSH/ Free T4/ Antiviral Testing:** will be performed at local laboratories according to the laboratory's normal procedures. Laboratory tests required are provided in Section 6.5.9.
- k. **Pharmacokinetic (PK) / Anti-Drug Antibody (ADA):** Blood sample collection timings for SL-172154 PK/ADA measurement are outlined in Section 6.1.1. Blood volumes required will be provided in the Study Lab Manual (SLM). PK/ADA samples should not be collected from infusion port for drug delivery i.e., recommend having a separate line in the opposite arm for sample collection.
 1. If a subject discontinues SL-172154 due to IRR and continues on PLD monotherapy, to the extent feasible, an additional ad-hoc ADA sample should be collected at a subsequently scheduled visit.
 2. All subjects should have just one additional blood sample collected for SL-172154 ADA assessment within 45-90 days of last dose of SL-172154 study treatment.
- l. **Cytokines and Receptor Occupancy:** Blood sample collection timing for cytokine and receptor occupancy assessments are outlined in Section 6.1.1. Blood volumes required will be provided in the SLM. Cytokine samples should not be collected from infusion port for drug delivery i.e., recommend having a separate line in the opposite arm for sample collection.

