6.5.9.2 Pregnancy Testing

All FCBP subjects must have a negative pregnancy test (serum or urine) at Screening. A separate assessment is required if a negative Screening pregnancy test is obtained more than 72 hours before the first dose of SL-172154. Subjects with a positive pregnancy test must be excluded from the study. Subjects with a negative pregnancy test result must agree to use an effective contraception method as described in Appendix Section 16.2.

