16.2 Contraception Requirements

Definition of Female of Childbearing Potential (FCBP)

A female subject who is not sterile due to surgery (i.e., from bilateral tubal ligation/occlusion, bilateral oophorectomy, bilateral salpingectomy, or complete hysterectomy) or who does not have a congenital or acquired condition that prevents childbearing or who is not naturally postmenopausal for at least 12 consecutive months.

Definition of Female of Non-Reproductive Potential

Female subjects will be considered of non-reproductive potential if they:

1. Are postmenopausal if defined as amenorrheic for 12 consecutive months without an alternative medical cause. In women < 50 years of age and/or perimenopausal, a high follicle stimulating hormone (FSH) level in the postmenopausal range may be used to confirm a postmenopausal state in women not using hormonal contraception or hormonal replacement therapy. In the absence of 12 consecutive months of amenorrhea, a single FSH measurement is insufficient.

OR

2. Have had a hysterectomy and/or bilateral oophorectomy, bilateral salpingectomy, or bilateral tubal ligation/occlusion, at least 6 weeks prior to screening.

OR

3. Have a congenital or acquired condition that prevents childbearing.

Highly Effective Methods of Contraception (< 1% failure rate)

A highly effective method of contraception is defined as one that results in a low failure rate (i.e., less than 1% per year) when used consistently and correctly. For contraception, subjects should comply with one of the following:

1. Practice abstinence† from heterosexual activity

OR

2. Use (or have their partner use) acceptable contraception during heterosexual activity.

Acceptable methods of contraception are‡:

- Single method (one of the following is acceptable):
 - intrauterine device (IUD)
 - vasectomy of a female subject's male partner
 - contraceptive rod implanted into the skin

- Combination methods
 - Female subjects: the following hormonal contraceptive methods (stable dose at least 3 months prior to first dose of study treatment) may be used by female subjects and requires use of a male condom for the male partner:
 - oral contraceptive pill (estrogen/progestin pill or progestin-only pill)
 - subcutaneous contraceptive injection
 - contraceptive skin patches
 - vaginal contraceptive rings
 - contraceptive implants into skin

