†Abstinence (relative to heterosexual activity) can be used as the sole method of contraception if it is: (1) consistently employed during the entire period of risk associated with the administered drugs; (2) consistent with the subject's preferred and usual lifestyle; and (3) considered acceptable by local regulatory agencies and IRBs/IECs. Periodic abstinence (e.g., calendar, ovulation, sympto-thermal, postovulation methods) and withdrawal are not acceptable methods of contraception.

‡If a contraceptive method listed above is restricted by local regulations/guidelines, then it does not qualify as an acceptable method of contraception for subjects participating at sites in this country/region.

Subjects should be informed that taking SL-172154, PLD, or MIRV may involve unknown risks to the fetus (unborn baby) if pregnancy were to occur during the study. To participate in the study, subjects of childbearing potential must adhere to the contraception requirement (described above) starting at least 14 days prior to the first dose of study treatment, during treatment, and through at least 6 months (or for the duration required by local regulatory guidance) after the last dose of PLD or at least 3 months after the last dose of MIRV or SL-172154, whichever is longer.

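### Criterion 14 requires two contraceptive methods where Appendix 16.2 accepts one, and Section 6.5.9.2 triggers a repeat pregnancy test that neither schedule lists

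*Protocol*

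**What the plan says.** **Contraception.** Protocol Section 4.1, criterion 14, repeated in the synopsis, reads: "FCBP must use 2 highly effective methods of contraception starting at least 14 days prior to the first dose of study treatment". In Section 4.1 the criterion closes with a cross-reference: "See Appendix Section 16.2 for further details regarding effective methods of contraception".

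Appendix 16.2, in its part on highly effective methods, says: "For contraception, subjects should comply with one of the following". The two options are abstinence or acceptable contraception. Under the second comes "Single method (one of the following is acceptable", followed by an intrauterine device, vasectomy of the partner, or an implanted contraceptive rod. Abstinence "can be used as the sole method of contraception if it is" practised under three stated conditions. Section 6.5.9.2 says that subjects with a negative pregnancy test "must agree to use an effective contraception method as described in Appendix Section 16.2".

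**Pregnancy testing.** Criterion 14 asks for a negative test no more than 4 days from the first dose of study treatment. Section 6.1, footnote i, places the screening test "within 4 days of the first dose of PLD on Cycle 1 Day 1". Section 6.2, footnote k, sets the same limit against the first dose of mirvetuximab soravtansine (MIRV). Both footnotes name Cycle 3 Day 1 (C3D1) as the next test. Section 6.5.9.2 adds: "A separate assessment is required if a negative Screening pregnancy test is obtained more than 72 hours before the first dose of SL-172154". SL-172154 is first given on Cycle 1 Day 8 (C1D8) in both regimens (Sections 3.2.1 and 3.2.2).

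The SAP adds nothing on either rule, but its Section 6.2 plans a separate listing of subjects who do not meet eligibility criteria.

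**The concern.** A site that checks eligibility against Section 4.1 and a site that checks it against the appendix can reach opposite answers for the same subject. Section 4 does not permit waivers and Section 14.4 requires deviations to be reported. A subject enrolled on one method would therefore be recorded as an eligibility deviation or not, depending on the page used. The SAP listing of unmet criteria would inherit that ambiguity.

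On testing, a site that follows its schedule exactly, as Section 6 requires, will miss a test that Section 6.5.9.2 also requires. Appendix 16.2 says that all three drugs may carry unknown fetal risk, so both rules exist to protect participants and should be unambiguous.

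**Working it through.** The plan gives no figure to reproduce. The check is a side-by-side reading and some calendar arithmetic.

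**Contraception: what each place requires**

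| Place in the Protocol | Requirement | Subject using only an intrauterine device |
|---|---|---|
| Synopsis and Section 4.1, criterion 14 | Two highly effective methods | Not eligible |
| Appendix 16.2 | One option; a single listed method or abstinence suffices | Compliant |
| Section 6.5.9.2 | One effective method, as in Appendix 16.2 | Compliant |

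Could the appendix be a menu from which criterion 14 takes two items? Its wording is against this. It tells subjects to follow one option. It accepts abstinence as a sole method. It closes by making adherence to the requirement it has just described a condition of participation, with the same 14-day lead-in and the same 6-month and 3-month minimum periods after treatment as criterion 14. It reads as a complete rule. The only route in it that pairs two methods is hormonal contraception with a male condom.

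Within the appendix, an implanted contraceptive rod is in the single-method group, while contraceptive skin implants are in the group that also needs a condom. The terms are not identical, but they overlap and the text does not separate them.

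**Pregnancy test: the two limits on one time axis**

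Inputs:
- Criterion 14 and both schedules: test 0 to 4 days before the Cycle 1 Day 1 (C1D1) dose; 4 × 24 = 96 h.
- First SL-172154 dose on C1D8: 8 − 1 = 7 days after C1D1; 7 × 24 = 168 h, nominal.
- Limit in Section 6.5.9.2: 72 h before that dose.

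Interval from a valid screening test to the first SL-172154 dose:
- test on C1D1, immediately before dosing: 168 + 0 = 168 h;
- test 4 days earlier: 168 + 96 = 264 h.

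The whole range, 168 to 264 h, exceeds 72 h. The 72-hour window opens 168 − 72 = 96 h after the C1D1 dose, whereas the criterion 14 window has closed by that dose. The two do not overlap, so no single test can satisfy both.

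Visit flexibility does not change this. Even if the general 3-day assessment window in the schedules were applied to the Day 8 visit, the shortest interval would be 168 − 72 = 96 h, still above 72 h. A later Day 8 visit lengthens the interval.

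The pregnancy-test rows in Sections 6.1 and 6.2 show screening, then Cycle 3 onward, then the post-treatment visit. The repeat that Section 6.5.9.2 triggers is on neither.

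**The case against.** **Section 4 locates eligibility in Sections 4.1 and 4.2, so the stricter text governs.** This has some force: criterion 14 cites the appendix only for further detail, and a site can treat Section 4.1 as controlling. But the appendix sets its own condition for participation, and Section 6.5.9.2 sends sites there for the requirement. The conflict in wording stands, most plainly for abstinence alone and for the single methods.

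**The testing rules add to each other.** This is right, and it limits the point. A reader might infer from the two anchors that a subject passes or fails according to the page used for the test as well. The documents do not support that. Section 6.5.9.2 asks for a second assessment and sets no competing entry window, so testing twice satisfies every page. A reader might also infer that testing before first exposure differs between pages. It does not: criterion 14 and both schedules agree on the 4-day limit before pegylated liposomal doxorubicin (PLD) or MIRV on C1D1, and the extra test precedes only the later SL-172154 dose.

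**The gap is easily filled.** Both schedules already have a C1D8 clinic visit with blood sampling, and Section 6.12 allows additional visits. The visit exists; the pregnancy-test entry is missing.

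**Few subjects are affected.** Plausible. Appendix 16.2 removes postmenopausal and surgically sterile women from the definition, and Section 1.2 describes debulking surgery as part of front-line care for advanced disease.

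**Conclusion.** Two inconsistencies in current text stand. First, the contraception requirement is two methods in criterion 14 and the synopsis but one in Appendix 16.2 and Section 6.5.9.2, so a subject using one listed single method, or abstinence alone, meets one text and fails the other. The two implant entries add a smaller conflict inside the appendix. Second, Section 6.5.9.2 triggers a repeat pregnancy test for every subject of childbearing potential treated on schedule (168 to 264 h against 72 h), and neither schedule lists it. The second defect is an unscheduled required test, not an eligibility split.

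The size in subjects cannot be given. The documents do not state how many will be of childbearing potential, so on their face it could be anywhere from none to all of the approximately 102. I assume a minority, given the definition and the disease. The effect is on participant protection, consistency between sites and deviation records. No endpoint, dose-limiting toxicity rule, sample size or analysis is affected. The timing result assumes the nominal Day 1 and Day 8 schedule. Nothing here says which contraception or testing rule is right.

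**What to change.** Reconcile the synopsis, criterion 14 in Section 4.1, Section 6.5.9.2 and Appendix 16.2 to one contraception requirement, and make the two implant entries in the appendix consistent. Reconcile Section 6.5.9.2 with the schedules in Sections 6.1 and 6.2, either by entering the repeat test in both schedules or by aligning the Section 6.5.9.2 wording with them. The sponsor's clinical team should choose in each case. The statistical review has no basis for preferring one method or two, or for removing or keeping the second test.

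The cost is a clarification memo now and matching text in the next amendment. If the repeat test is kept, it is one pregnancy test per affected subject, already required by Section 6.5.9.2, and the existing C1D8 visit could accommodate it. No SAP change is needed, but the rule should be settled before deviations are classified for the SAP Section 6.2 listings.

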4.2 Exclusion Criteria

Subjects are excluded from the study if any of the following criteria apply:

1. Prior treatment with a SIRP α targeting agent, anti-CD47 agent or CD40 agonist.
2. [PLD Cohort] Prior treatment with doxorubicin or PLD.
3. [MIRV Cohort] Prior treatment with MIRV or another FR α -targeting agent.

4. Any anti-cancer therapy within the time intervals noted below prior to first dose (Day 1) of study treatment:

Therapy	Washout period
Chemotherapy	4 weeks or 5 half-lives, whichever is shorter
Hormonal therapy	4 weeks or 5 half-lives, whichever is shorter
PD-1/L1 inhibitor and other immunotherapies not otherwise specified	4 weeks or 5 half-lives, whichever is shorter
Tumor vaccine	4 weeks
Cell-based therapy	8 weeks
Other mAbs or biologic therapies	4 weeks or 5 half-lives, whichever is shorter
Other investigational agents not covered above	4 weeks or 5 half-lives whichever is shorter
Major surgery	2 weeks
Radiation (except palliative intent which does not require washout)	2 weeks

5. Concurrent chemotherapy, immunotherapy, biologic or hormonal therapy for cancer treatment is prohibited. Concurrent use of hormones for non-cancer-related conditions is acceptable.

6. Receipt of live attenuated vaccine (including live attenuated vaccines for COVID-19) within 28 days of the first dose of study treatment.

7. Current or prior use of systemic immunosuppressive medication within 7 days prior to first dose of study treatment. The following are exceptions to this exclusion criterion:

- Intranasal, inhaled, topical, injected (e.g., intra-articular injection) or local steroid or immunosuppressive medication.
- Steroids as premedication for HSRs (e.g., CT scan premedication).

8. **[MIRV Cohort]** Requires use of folate-containing supplements (e.g., folate deficiency).

9. Active or documented history of autoimmune disease that has required treatment with a disease modifying agent or immunosuppressive therapy in the past two years, history of multiple sclerosis (MS) or other demyelinating disease and/or Lambert-Eaton syndrome (paraneoplastic syndrome). Exceptions include controlled Type I diabetes, vitiligo, alopecia areata or hypo/hyperthyroidism.

10. Ongoing or active infection (e.g., no systemic antimicrobial therapy for treatment of infection within 5 days of D1 of study treatment).

11. Known severe hypersensitivity to the active drug substance or to any of the excipients for the agents to be administered or subjects with known hypersensitivity to Chinese hamster ovary cell products. Prior severe hypersensitivity to monoclonal antibodies **[MIRV Cohort only]** or liposomal preparations **[PLD Cohort only]**.

12. Severe gastrointestinal conditions such as clinical or radiological evidence of bowel obstruction within 4 weeks prior to study entry.

13. Clinically significant or uncontrolled cardiovascular disease including any of the following:

- Myocarditis
- Unstable angina within 6 months from first dose of study treatment
- Acute myocardial infarction within 6 months from first dose of study treatment
- Uncontrolled hypertension
- NYHA Class III or IV congestive heart failure
- Clinically significant (symptomatic) cardiac arrhythmias (e.g., sustained ventricular tachycardia, second- or third- degree atrioventricular block without a pacemaker, circulatory collapse requiring vasopressor or inotropic support, or arrhythmia requiring therapy)
- History of hemorrhagic or ischemic stroke within 6 months prior to enrollment
- Prior anthracycline-related cardiotoxicity or prior anthracycline exposure approaching the lifetime limit **[PLD cohort only]**

14. **[MIRV Cohort]** History of cirrhotic liver disease (Child-Pugh Class B or C).
15. **[MIRV Cohort]** Active or chronic corneal disorders, history of corneal transplantation, or active ocular conditions requiring ongoing treatment/monitoring, such as uncontrolled glaucoma, wet age-related macular degeneration requiring intravitreal injections, active diabetic retinopathy with macular edema, macular degeneration, presence of papilledema, and/or monocular vision.
16. Previous clinical diagnosis of noninfectious interstitial lung disease (ILD), including noninfectious pneumonia.
17. Untreated central nervous system (CNS) or leptomeningeal metastases. Subjects with treated CNS metastases must have completed definitive treatment (radiotherapy and/or surgery) > 2 weeks prior to first dose of study treatment and no longer require steroids.
18. Women who are pregnant or breast feeding, or who plan to become pregnant or breast feed while receiving study treatment.
19. Psychiatric illness/social circumstances that would limit compliance with study requirements and substantially increase the risk of AEs or compromised ability to provide written informed consent.
20. Another malignancy that requires active therapy and that, in the opinion of the investigator and Sponsor, would interfere with monitoring of radiologic assessments of response to the study treatment.
21. Has undergone allogeneic stem cell transplantation or organ transplantation.
22. Known history or positive test for human immunodeficiency virus (HIV), or positive test for hepatitis B (positive for hepatitis B surface antigen [HbsAg]) or hepatitis C virus ([HCV]; if HCV antibody (Ab) test is positive check for HCV RNA).

NOTE: *Hepatitis B virus (HBV):* Subjects who are hepatitis B core antibody [HbcAb] positive, but HbsAg negative are eligible for enrollment. *HCV:* Subjects who are HCV Ab positive, but HCV RNA negative are eligible for enrollment.

